Child Outcome Measures at Time 3: An adapted version of the Infant Toddler Social Emotional Assessment (ITSEA; Carter & Briggs-Gowan, 2006), comprised of the full Brief Infant Toddler Social Emotional Assessment (BITSEA) and select additional scale items from the longer ITSEA instrument, was developed in consultation with the scale’s author. The instrument measures both social-emotional/ behavioral problems and delays in competency for children ages 12-36 months. It is a 71-item parent-report index constituting of six sub-scales: Problem behavior, competence, compliance, negative emotionality, aggression, and sleep.

5. Sample size justification:

We employed a computer program provided by Murphy et al. (2009; the same information is available from the tables in Cohen, 1988) to compute the significance level required for a projected sample size, incorporating attrition estimates, of $N=120$ (60 each in the treatment and control groups, respectively). Assuming the null effect hypothesis and alpha set at .05 and power of .8, an $F(1, 117)$ of 7.74 with a $d = .514$ is required for significance. Keeping the null hypothesis test, alpha .05 and lowering power to .5, an $F(1, 117) = 4.03$ with a $d = .37$ is required for significance. Drawing on effect size estimates from the feasibility study, even with low power (.5) resulting in a $d=.37$ we would be positioned to establish the effect of the FIOC treatment for 10 of the 12 FIOC variables (10 of the 12 SCID-evaluated couple problem-solving and communication variables summarized earlier had a d greater than .33).

6. Sample type or inclusion and exclusion criteria for participating in the research:

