## **Cover Letter**

### **Statistical Analysis Plan**

**Document Date 1.31.2022**

**NCT03097991**

### **FIOC Statistical Analysis Plan**

- Initial descriptive summations and simple statistical tests will compare groups.

- Primary Aims 1-4: Effects of the intervention. To examine if coparenting and individual adjustment outcomes are superior for FIOC families than for control group families at 3- and 12-months post-partum two-sided independent sample t-test for equivalence will first be employed for single time point comparisons. We will test hypotheses further using linear or generalized linear models to control for potential confounding and account for imbalance between the two treatment conditions.
- For longitudinal outcomes that are continuous (measured at Baseline; 3; and 12 months post-partum) we will use repeated measures analysis of covariance (ANCOVA; Crowder & Hand, 1990) to detect if treatment and control groups perform differently at any time points. For longitudinal outcomes that are categorical, generalized linear model (GLM, McCullagh & Nelder, 1989) will be used for the same purpose. Repeated measures ANCOVA and GLM allow us to account for correlation between repeated measures and detect possible moderating/confounding between treatment effects and subject individual differences. Multiple comparison adjustment will be addressed in analyses. We will report significance under both regular (.05) and Bonferroni-adjusted alpha.
- Exploratory Aim 1: To examine whether extent of father engagement is associated with better infant socioemotional adjustment regression analyses will examine variance in infants' 12-month ITSEA Internalizing, Externalizing, Dysregulation and Competence scores explained by 3- and 12-month father engagement.
- Exploratory Aim 2: To examine whether FIOC prevents the emergence of IPV and help to prevent future IPV in couples where it was previously reported, we will first explore simple chi-square analysis to compare FIOC and TAU conditions on the binary variable of any instance of physical violence between partners reported on the CTS2 over the 12 months of follow-up. Next,

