we will conduct a linear regression model with intervention group and baseline CTS2 scores as predictors and CTS2 12-month scores as outcome variables. Next, hierarchical regression will be used to assess the main effects of the intervention group and severity of previous violence (reported on the CTS2 at baseline) on the severity of IPV over the 12 months of follow-up, and the interaction effect of FIOC x previous IPV on IPV severity at follow-up.

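### For continuous outcomes measured at baseline, 3 and 12 months, the SAP leaves open baseline's role, the contrast and the handling of missed visits; its sentence on GLM and correlation also needs correcting

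*SAP*

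**What the plan says.** The SAP's longitudinal bullet opens "For longitudinal outcomes that are continuous (measured at Baseline; 3; and 12 months post-partum" and assigns these outcomes to repeated-measures ANCOVA. The stated purpose is "to detect if treatment and control groups perform differently at any time points". No covariate, model term or covariance structure is named. The bullet continues "For longitudinal outcomes that are categorical, generalized linear model" for the same purpose, and then says of both methods: "Repeated measures ANCOVA and GLM allow us to account for correlation between repeated measures".

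Three other places bear on this.

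- The SAP bullet on Primary Aims 1-4 runs simple tests before any model: "two-sided independent sample t-test for equivalence will first be employed for single time point comparisons". (The word equivalence there is a separate matter.)
- Exploratory Aim 2 does fix baseline's role, but only for the CTS2: "linear regression model with intervention group and baseline CTS2 scores as predictors and CTS2 12-month scores as outcome variables".
- Protocol section 5 bases power on 120 families, a figure described as "incorporating attrition estimates", and quotes F statistics on 1 and 117 degrees of freedom.

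Protocol section 1 assigns the families after the first 150, up to 170, to FIOC without randomization, because the two groups need to be balanced on postnatal follow-up. Neither document gives a rule for analysing a family that misses a visit.

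**The concern.** Three choices that affect the result are left to the analyst.

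**Missed visits.** Classical repeated-measures ANCOVA needs every occasion. A family seen at 3 months but not at 12 would drop out of the longitudinal model, though it stays in the single-visit t-test. The two analyses of one outcome would then rest on different families. The protocol expects losses and has already acted on unequal follow-up, so the question will arise.

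**Baseline and contrast.** If baseline is a covariate, the test compares adjusted postnatal scores. If it is an occasion, the natural test is group-by-time, in effect a comparison of changes. These differ in power. If baseline counts as a time point, a chance baseline difference would even satisfy the SAP's stated purpose. A choice left open can also be made after the data are seen.

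**The GLM sentence.** A generalized linear model as named treats records as independent. No GEE, random effect or clustered variance is mentioned, so an analyst who follows the text literally could fit a model that ignores the correlation.

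The baseline question does not apply to outcomes first measured at 3 months, such as parenting stress, the Parenting Alliance Measure and coparenting in the trilogue play.

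**Working it through.** **Inputs.** From protocol section 5: 60 per arm, two-sided alpha .05, F = 7.74 with d = .514 at power .80, and F = 4.03 with d = .37 at power .50. The documents give no within-person correlation and no loss rate per visit. I assume a common correlation rho of .3, .5 or .7, equal standard deviations at all visits, and the loss rates shown below.

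**The plan's own figures.** d = 2 x sqrt(F/117) gives .514 for F = 7.74 and .371 for F = 4.03. With noncentrality d x sqrt(60/2), power is .797 at d = .514 and .520 at d = .37. Both agree with the protocol to within about two points. The degrees of freedom are 120 - 2 - 1 = 117, which fits two groups plus one covariate; a two-group t-test would have 118.

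**Power by role of baseline (d = .37, 60 per arm, complete data).** Standardized effects:

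- one visit, adjusted for baseline: d / sqrt(1 - rho^2), 117 df
- one visit, change from baseline: d / sqrt(2 - 2 rho), 118 df
- mean of both visits, adjusted: d / sqrt((1 + rho)/2 - rho^2)
- mean of both visits, change: d / sqrt((1 + rho)/2 + 1 - 2 rho)

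| Contrast | rho .3 | rho .5 | rho .7 |
|---|---|---|---|
| One visit, adjusted | .56 | .64 | .80 |
| One visit, change | .40 | .52 | .74 |
| Mean of two visits, adjusted | .77 | .81 | .92 |
| Mean of two visits, change | .50 | .64 | .85 |

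The unadjusted one-visit t-test has power .52 throughout. Below rho = .5 a change score therefore does worse than ignoring baseline.

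**Families kept (m3 and m12 are the assumed proportions missing each visit).** If losses are independent, the share with both visits is (1 - m3)(1 - m12) and the share with at least one is 1 - m3 x m12. If losses are nested, the shares are 1 - max(m3, m12) and 1 - min(m3, m12).

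| m3, m12 | Both visits (independent / nested) | At least one (independent / nested) |
|---|---|---|
| 20%, 30% | 56% / 70% | 94% / 80% |
| 10%, 20% | 72% / 80% | 98% / 90% |

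**Size of a plain GLM over two visits, nominal 5%.** The nearest match to the SAP's purpose is a joint test of a difference at either visit. Its size is P[(1 + rho) X1 + (1 - rho) X2 > 5.991], with X1 and X2 independent chi-square on 1 df. This gives 5.3%, 6.0% and 6.8% for rho .3, .5 and .7. For comparison, 2 x (1 - Phi(1.96 / sqrt(1 + rho))) for a group effect pooled over visits gives 8.6%, 11.0% and 13.3%. With 1 - rho in place of 1 + rho, a group-by-visit test gives 1.9%, 0.6% and under 0.1%. Single-visit tests are unaffected.

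**The case against.** The best defence is that this is loose wording around a sound intention. The SAP plainly means to handle the correlation, and repeated measures can be read as qualifying both ANCOVA and GLM. It names no categorical longitudinal outcome: the one explicitly binary outcome, any physical violence over the 12 months, is a single value tested by chi-square. Most repeated outcomes in the protocol are scale scores, and the coded infant categories are only possible candidates. This largely stands, and it reduces the GLM point to a wording correction.

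A reader might infer that the trial faces a false-positive rate of 9 to 13%. The documents do not support that. Those figures belong to a pooled group effect that neither document proposes, fitted to outcomes that the SAP does not name.

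A reader might also infer that change scores will be analysed. No passage specifies that. The name ANCOVA, the 117 degrees of freedom and the CTS2 model all lean towards baseline as a covariate. Against them, the SAP lists baseline among the measured occasions, and protocol Hypothesis 2 is worded as a greater decrease in depressive symptoms. The lean is real, but the SAP does not fix the choice for Aims 1-4.

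Last, the SAP does not say that incomplete families will be dropped. That follows from the classical method, and nothing in the plan overrides it. The power comparison also assumes complete data, so it sizes the choice of contrast and not the loss from missed visits.

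**Conclusion.** The concern holds as an under-specified analysis that should be tightened. For continuous outcomes with a baseline, the SAP leaves open baseline's role, the model term to be tested and the treatment of families missing a visit. At the protocol's d = .37, the choice between adjustment and change moves one-visit power by 16, 12 and 6 to 7 points at rho .3, .5 and .7. That matters in a plan that contemplates power near .5.

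Complete-case use could discard families with one usable postnatal score. How many depends on loss rates that the documents do not give, and any resulting bias cannot be sized from them.

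The sentence on GLM and correlation is incorrect as written and secondary in weight. Under the assumed correlations, the joint two-visit test would run at about 5.3 to 6.8%. All of these figures rest on assumed correlations.

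**What to change.** **Continuous repeated outcomes.** Analyse the 3- and 12-month scores with a likelihood-based linear mixed model. Include arm, visit, arm by visit, the baseline score where one was measured, and the urn factors (children from prior unions, IPV frequency), with unstructured visit covariance. Use every randomized family with at least one postnatal score.

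**Contrast.** State it in advance, as the arm difference at 3 and at 12 months or as their average, and quote power for that contrast.

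**Analysis set.** Restrict the main model to the urn-randomized families, that is, the first 150. Show the families assigned to FIOC without randomization only in a separate sensitivity analysis.

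**Categorical repeated outcomes.** Name any that exist, specify GEE clustered on family or a generalized linear mixed model, and correct the sentence on correlation.

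**Cost.** No new data are needed, only SAP wording and slightly more model set-up. The mixed model assumes that missingness is explained by the observed data; standard GEE needs a stronger assumption. Up to 170 - 150 = 20 families leave the main comparison, which gives up some of the numbers the protocol added to support power.

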- Aim 1: To determine the efficacy of FIOC in positively affecting first-year coparenting of unmarried African American parents, relative to early coparenting of comparison families
Hypothesis 1: Families who participate in FIOC will demonstrate more cooperation and better communication in their post-natal coparenting systems at 3 and 12 months post-partum than families receiving TAU
- Aim 2: To determine the efficacy of FIOC in affecting first-year parental adjustment.
Hypothesis 2: Mothers and father who participate in FIOC will show greater decreases in depressive symptomology from prenatal to postnatal assessments than parents receiving TAU.
Hypothesis 3: Mothers and father who participate in FIOC will show lower levels of parenting stress at 3 and 12 months than families receiving TAU.
- Aim 3: To determine the efficacy of FIOC in affecting early child outcomes.
Hypothesis 4: Infants whose coparents participate in FIOC will show a more advanced

triangular capacity at 3 and 12 months

Hypothesis 5: Infants whose coparents participate in FIOC will show better regulatory and socioemotional competence at 12 months than control group children.

- Aim 4: To determine the efficacy of FIOC in affecting father involvement
Hypothesis 6: Fathers who participate in FIOC will show greater involvement at 3 and 12 months post-partum
- Aim 5: To determine whether increased father involvement is associated with better socioemotional adjustment by the baby
Hypothesis 7: Children of more involved fathers will show greater regulatory and socioemotional competence at 12 months post-partum
- Aim 6: To explore whether the FIOC intervention has an impact on the emergence of intimate partner violence (IPV)
Hypothesis 8: IPV will be more likely to emerge during the child's first year among TAU families than among families who complete the FIOC intervention
- Aim 7: To determine whether enrollment numbers, randomization rates, retention rates, and comparative RCT outcomes differ as a function of active versus passive recruitment methods for unmarried mother-father dyads.
Hypothesis 9: Proportions of enrollment and randomization and retention rates will favor families identified via self-referral (passive recruitment), while outcomes for families completing the intervention will not differentiate the two groups.

4. Study design including information needed to answer the research questions:

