Exclusion Criteria: Families will be excluded if they: 1) demonstrate evidence of psychotic symptoms or suicidal ideation on the Brief Symptom Inventory; 2) either partner has recently (over the past 12 months) been arrested and convicted for violence (assault) perpetrated against someone other than a current or former partner who is the co-parent of one of their children; or 3) are deemed high risk or in need of more intensive intervention. Risk determination is made by weighing the parent's report on the Danger Assessment Scale (DAS). As a rule of thumb, a DAS score of 9 or higher will result in automatic exclusion from the study. However, it is also possible that even with a score below 9, the parent may disclose one or more of the following issues during administration of the DAS, any of which would result in exclusion from the study: 1) parent reports she has required medical care because of significant injuries due to his violence, 2) parent says she fears for her life, 3) parent reports that the partner has threatened with a weapon and owns a gun or has a gun in the household; 4) parent reports that the partner has threatened to kill her; 5) parent reports that violence has escalated recently; 6) parent reports the partner's use of illicit drugs such as cocaine, methamphetamines, hallucinogens, or opiates .

7. Expected results of the research (reports, materials, discussion papers, contributions to theory):

Results will equip the research team with answers to study objectives and determine whether there would be value in studying the curriculum in a future multi-site implementation trial.

8. Study Staff

- 1. [name].**, P.I. Will provide all project oversight; serve as IRB officer; ensure research integrity and compliance; chair senior staff and other relevant team meetings; supervise fidelity-monitoring efforts; oversee proper implementation of all protocols, data collection, evaluation of videotaped infant and family data, data management and entry, analyses, report writing, and dissemination of findings.

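### The SAP reports Aim 1 significance at both .05 and a Bonferroni alpha without saying which decides efficacy or over which tests, and no primary coparenting measure or visit is named

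*SAP*

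**What the plan says.** Protocol Section 3 states Hypothesis 1 in general terms: FIOC families will show "more cooperation and better communication in their post-natal coparenting systems at 3 and 12 months post-partum than families receiving TAU". Section 4 describes three kinds of measure that bear on it:

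- SCID ratings of the mother-father discussion, at baseline, 3 and 12 months
- the Parenting Alliance Measure (PAM) from each parent, at 3 and 12 months
- observed coparenting in the Lausanne Trilogue Play (LTP), at 3 and 12 months.

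None of these, and neither visit, is called primary.

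Protocol Section 5 sizes the trial for a single comparison: "Assuming the null effect hypothesis and alpha set at .05 and power of .8", with N = 120, "60 each in the treatment and control groups, respectively". It then argues variable by variable, on the ground that "10 of the 12 SCID-evaluated couple problem-solving and communication variables summarized earlier had a d greater than .33".

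The SAP groups Aims 1-4 as primary. It plans two-sided t-tests at single time points, then models. For outcomes measured repeatedly it looks for a group difference at any time point. In that same bullet it promises that multiple comparisons will be addressed and adds "We will report significance under both regular (.05) and Bonferroni-adjusted alpha". It goes no further on multiplicity.

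**The concern.** Reporting two thresholds is not a decision rule. A coparenting result with p = .01 would be significant at .05 and, over 12 or 24 tests, not significant after Bonferroni. The SAP does not say which reading answers Aim 1. Nor is the Bonferroni alpha fixed, because the number of tests it divides by is not given.

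The choice matters in both directions. If unadjusted .05 is taken as sufficient, an ineffective programme has a sizeable chance of yielding at least one favourable coparenting result. If Bonferroni over a long list is taken as governing, the trial loses much of the power on which Section 5 relies. Which of these applies could be settled after the results are known.

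**Working it through.** **1. Reproduce the planned figures.** Inputs from Protocol Section 5: 60 per arm, alpha .05, F(1, 117) = 7.74 at power .8.
- d = 2 × sqrt(7.74/117) = .514, as stated.
- Power at d = .514 (noncentral F with 1 and 117 df, noncentrality .514² × 60/2 = 7.93, two-sided alpha .05) is 79.7%.

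The sample size is therefore right for one test at .05.

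**2. Count the tests.** The documents give no count, so two are used.
- *Modest count, 12.* Section 4 names three SCID ratings (problem-solving communication, cohesion, coerciveness). Adding PAM from two parents and one LTP score gives 3 + 2 + 1 = 6 measures, × 2 visits = 12.
- *Larger count, 24.* Section 5 refers to 12 SCID variables; × 2 visits = 24. This is an inference: 12 is a feasibility-study count that Section 5 carries into this trial.

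**3. Chance of a false favourable result.** Under the null, a two-sided p<.05 in FIOC's favour has probability .025 per test. For k independent tests the chance of at least one is 1 − .975^k:
- k = 12: 1 − .975^12 = 26.2%
- k = 24: 1 − .975^24 = 45.5%

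The outcomes will be correlated, and the documents give no correlations. With a common correlation ρ between test statistics, the chance is 1 − ∫ φ(g) × Φ((1.96 − √ρ·g)/√(1−ρ))^k dg. The values of ρ are assumptions.

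| Tests | ρ = 0 | ρ = .5 | ρ = .7 |
|---|---|---|---|
| 12, favouring FIOC | 26% | 16% | 12% |
| 24, favouring FIOC | 46% | 23% | 16% |
| 12, either direction | 46% | 32% | 23% |
| 24, either direction | 71% | 46% | 31% |

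The benchmark for a single test is 2.5% favouring FIOC and 5% in either direction. Only the favourable rows bear on a false claim of efficacy.

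**4. Power if Bonferroni governs.** Same 60 per arm and d = .514:

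| Confirmatory tests | Alpha per test | Power per test |
|---|---|---|
| 1 | .05 | 79.7% |
| 3 | .0167 | 65% |
| 12 | .0042 | 46% |
| 24 | .0021 | 37% |

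Over 24 tests, the effect detectable with 80% power rises to about d = .73. Keeping 80% power at d = .514 would need about 117 per arm.

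**The case against.** The strongest reply is that the SAP does address multiplicity. Showing both thresholds is transparent, and a reader can see which findings fail correction. The verb is also report, not declare, and the sentence sits in the bullet on longitudinal outcomes. A reader might infer that every result in the trial is to be declared significant at both levels; the text does not say that. What stands against the reply is that no governing threshold is named. If the sentence covers only the longitudinal bullet, the single-visit t-tests have no stated adjustment at all.

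The count of 24 is also open to challenge. SCID is measured at baseline and both follow-ups, so one repeated-measures group test per variable would give 12 SCID tests, not 24. Counting only the three named SCID ratings at two visits gives 6 tests, with a 14% chance of a false favourable result if independent (10% at ρ = .5). Hypothesis 1 could also be read as requiring a difference at both visits, which would lower the error further, but the SAP does not impose that. These points lower the figure. Every count considered above still exceeds 2.5%.

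It is tempting to quote 71% as the chance of a wrong efficacy claim. That figure includes results favouring control, which cannot support efficacy, and it assumes 24 independent tests.

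A reader might also infer that a go/no-go decision hangs on these p-values. Protocol Section 7 says only that results will help "determine whether there would be value in studying the curriculum in a future multi-site implementation trial". It ties that judgement to no test or threshold.

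**Conclusion.** The concern holds in this form: the threshold that decides Aim 1, the family it covers, and the primary measure and visit are all unspecified. The plan as written therefore permits an efficacy claim at unadjusted .05. The resulting chance of at least one false favourable result is about 12% to 26% on the modest count of 12 tests and about 16% to 46% on the inferred count of 24, for assumed correlations from .7 down to 0. Strict Bonferroni over 24 tests would leave about 37% power at the planned effect. The documents show neither that the sponsor intends to rely on the unadjusted results nor that 24 tests are fixed. The defect is that nothing rules out either extreme.

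**What to change.** Amend the SAP to state that:

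1. the multiplicity-adjusted result decides each primary aim, with Holm in place of Bonferroni (same familywise protection, never less powerful);
2. unadjusted .05 results are descriptive;
3. the rule also covers the single-time-point tests;
4. the Aim 1 family is a named list of measures and visits, with a statement of whether one or all members must succeed.

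The sponsor should choose the family and keep it small, or use a single composite. One measure at one visit keeps the stated power of about 80%. Three ratings tested at .05/3 have about 65% power each at d = .514. The three SCID ratings named in Section 4 are one option, but the protocol presents them there as feasibility findings, not as this trial's primary outcomes. Confirming at 12 months only would set aside the 3-month half of Hypothesis 1.

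The change costs wording only: no new data or participants. It has two downsides. Isolated nominal findings can no longer be presented as confirmatory, and power per test falls once there is more than one confirmatory test. It should be made before results by arm are examined. The SAP is dated January 2022 and the documents do not show whether that has happened. If results by arm have already been seen, the Aim 1 choice should be labelled post hoc.

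### The Bonferroni report in the SAP would be better as Holm-adjusted p-values within a declared family, with the decisive result named and the power in protocol Section 5 labelled as unadjusted

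*SAP*

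**What the plan says.** The SAP's bullet on longitudinal outcomes says that multiple comparisons will be addressed and then gives one rule: "We will report significance under both regular (.05) and Bonferroni-adjusted alpha". Bonferroni is the only adjustment named. The SAP does not say which outcomes, visits or reporters (mother, father) form the family, how many tests it holds, or which of the two reports decides whether a hypothesis is supported.

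Section 5 of the protocol (sample size justification) projects 120 analysable families, "60 each in the treatment and control groups, respectively", a figure described as "incorporating attrition estimates". It gives two power statements, both at the full .05:

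- The first begins "Assuming the null effect hypothesis and alpha set at .05 and power of .8". Section 5 pairs this with F = 7.74 on 1 and 117 degrees of freedom, and a detectable effect of d = .514.
- The second begins "Keeping the null hypothesis test, alpha .05 and lowering power to .5". Here the pair is F = 4.03 and d = .37.

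Its working argument uses the second: "even with low power (.5) resulting in a $d=.37$ we would be positioned to establish the effect of the FIOC treatment for 10 of" twelve SCID variables. Section 5 does not mention multiplicity.

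**The concern.** There are two linked issues.

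The first is the method. Bonferroni tests every outcome at .05/m, however many others have already been rejected. Holm begins at .05/m and relaxes the threshold after each rejection. It protects the familywise error equally well under any correlation, and rejects everything Bonferroni rejects and sometimes more. Section 5 expects effects on most of its 12 SCID variables, and a step-down method gains most when many effects are real. The adjusted report may therefore be giving up some power.

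The second is that the power statement and the adjusted report do not describe the same test. A reader who carries the 80% or 50% from Section 5 over to the adjusted results would be too optimistic for any family of two or more tests.

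Both depend on a gap in the SAP. Neither Bonferroni nor Holm can be applied until the family and m are fixed, and reporting two thresholds controls no error rate until one is named as decisive.

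**Working it through.** **Inputs.** From Section 5: n = 60 per group after attrition, alpha .05, d = .514 and d = .37. From the SAP: a two-sided test ("two-sided independent sample t-test for equivalence will first be employed for single time point comparisons"), read here as an ordinary test of difference. The family size m is not given. I assume m = 2, 6 and 12: 2 for a small family, 6 for Hypotheses 1 to 6 under Aims 1 to 4, and 12 for the SCID variables in Section 5.

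**Step 1: reproduce Section 5.** Converting its F values with d = 2√(F/117):

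- F = 7.74 gives d = .514
- F = 4.03 gives d = .371

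Power comes from the noncentral F(1, 117) with noncentrality λ = n·d²/2, at the .05 critical value of 3.92:

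- d = .514: λ = 60 × .2642/2 = 7.93, power 79.7% (normal approximation 80.4%)
- d = .37: λ = 60 × .1369/2 = 4.11, power 52.0%

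Both match the stated figures closely. A one-sided .05 would give about 88% at d = .514, so the calculation is two-sided at the full .05.

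**Step 2: the same calculation at .05/m.**

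| m | alpha per test | power, d=.514 | power, d=.37 | d for 80% power |
|---|---|---|---|---|
| 1 | .0500 | 80% | 52% | .516 |
| 2 | .0250 | 71% | 41% | .569 |
| 6 | .0083 | 55% | 26% | .645 |
| 12 | .0042 | 46% | 19% | .689 |

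This is the power of each test under Bonferroni, and of the first step under Holm. If all ten SCID variables had d = .37, the expected number established would be 10 × .52 = 5.2 unadjusted and 10 × .19 = 1.9 with Bonferroni at m = 12.

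**Step 3: Holm against Bonferroni.** Order the p-values p(1) ≤ … ≤ p(m), compare p(j) with .05/(m − j + 1), and stop at the first failure. Simulation used m = 12, 60 v 60, two-sided t on 118 df, and correlation .3 and .6 between outcomes:

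| Real effects | d | Average power per real effect, Bonferroni | Holm |
|---|---|---|---|
| 10 of 12 | .514 | 46% | 53% |
| 10 of 12 | .37 | 19% | about 22% |
| 6 of 12 | .514 | 46% | 49% |

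With ten real effects at d = .514, the chance of establishing all ten is 2-10% with Bonferroni and 10-24% with Holm. The chance of a false positive on the two null variables stays below 3% with Holm. The chance of at least one rejection is identical, because Holm's first step is the Bonferroni test.

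**Step 4: if the .05 report were treated as decisive.** For independent tests with no real effects, the chance of at least one false positive is 1 − .95^m: 26% at m = 6 and 46% at m = 12.

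**The case against.** The strongest reply is that Bonferroni is valid under any dependence, so preferring Holm is a refinement and not the correction of an error. That stands. Bonferroni also comes with simple simultaneous confidence intervals and Holm does not, so the extra power has a price.

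The second reply is that the numbers rest on inputs the plan does not give. The SAP states no m. Its adjustment sentence sits in the repeated-measures bullet, so the family could be as small as the time points. The protocol's description of the coparenting discussion measure names only three SCID ratings, and the 12 variables come from the feasibility study. The gain of 7 points needs ten real effects all at d = .514, which is close to a favourable case; Section 5 argues from d = .37. The calculation also uses single-time-point tests, whereas baseline adjustment and repeated measures could change power. All of this stands, and it is why the results are shown as a range.

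Some stronger readings are tempting but unsupported:

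- A reader might infer that the SAP adopts Bonferroni as its confirmatory rule. It reports two thresholds and commits to neither.
- A reader might infer that adjusted power is under 50%. At d = .514 that is so at m = 12 but not at m = 2 or m = 6.
- A reader might infer that Section 5 rests on 80% power. It openly argues from 50% at d = .37.
- A reader might infer that Holm would recover the lost power. It does not restore 80% at m = 12 in these scenarios, and it leaves the first rejection untouched.

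What the reply does not remove is that Section 5 ignores any correction, and that Holm never rejects less at the same familywise error.

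**Conclusion.** The point holds as a cheap improvement with a reporting gap attached. Using Bonferroni is not a mistake. Holm would give the adjusted report the same protection with equal or greater power: about 7 points in the favourable case and about 3 in the less favourable ones, assuming m = 12, 60 per group and correlations of .3 to .6.

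The power figures in Section 5 are correct for a single unadjusted test and describe nothing else. Any family of two or more lowers them, by an amount that depends on m: from 80% to between 71% and 46% at d = .514, and from 52% to between 41% and 19% at d = .37, for m from 2 to 12. These figures illustrate an assumed range and are not properties of the plan, because the plan does not define the family. The undeclared family and the missing decision rule come first; the choice between Holm and Bonferroni matters only once they are settled.

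**What to change.** In the SAP:

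1. Declare each family of tests and its size m, saying whether visits and mother and father reports count separately.
2. State whether the unadjusted or the adjusted result decides whether a hypothesis is supported.
3. Report Holm-adjusted p-values within each declared family in place of the Bonferroni-adjusted alpha, with unadjusted confidence intervals shown beside them and labelled as such.

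In Section 5 of the protocol, or in a SAP note referring to it, label the 80% and 50% figures as unadjusted. Add the power at .05/m for the declared m, at both d = .514 and d = .37. Do not insert 46% or d = .69 as fixed values, since they apply only if m is 12.

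The cost is a few sentences and one recalculation, with no new data. The downsides are the loss of simple simultaneous intervals and a less favourable power statement. The family and the decisive result should be fixed before outcomes are compared by group.
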